10.7. Study Drug Administration

<Concomitant drug: Lucentis®>

Lucentis® administration to be done as per Lucentis® drug labeling.

<Investigational drug: DE-122>

1. Prior to starting the injection procedure, DE-122 should have been prepared as described in [Section 10.4](#) and [Section 10.5](#), and the study eye should have been prepared as described in [Section 10.6](#).
2. If the subject is phakic, the entry site is 4.0 mm from the limbus. If the subject is pseudophakic or aphakic, the entry site is 3.5 mm from the limbus. A caliper may be used to identify the needle entry site. The entry site location for the investigational drug should be the same quadrant as the concomitant drug, but not at the same entry point.
3. Insert the needle perpendicular to the eye wall at the location specified in Step 2 ([Section 10.7](#)). The needle should be inserted until the tip is just visible through the dilated pupil. Note: If paracentesis is considered necessary, it should be performed after injection of the DE-122 and noted in the source documents.
4. Very slowly, inject the entire DE-122 dose volume (20 µL or 40 µL) and slowly withdraw the needle. Do not pull back on the plunger at any time prior to withdrawing the needle.
5. Briefly apply pressure for approximately 1 minute to the needle entry site with sterile cotton tipped applicator (may be skipped per Clinical Investigator's discretion).
6. Remove the eyelid speculum.
7. Patch the study eye at the Clinical Investigator's discretion.
8. Prescribe fluoroquinolone equivalent antibiotic eye drops three times/day for two days following injection, to be initiated as soon as possible.

<Investigational drug: Sham>

Sham is injection that simulates DE-122 drug administration. Sham intravitreal injections will be administered to subjects according to the same dosing schedule and procedure as DE-122 injections. However, the Sham intravitreal injection procedure will only mimic DE-122 intravitreal injection in that the blunt end of an empty syringe is pressed against an anesthetized eye, instead of a needle attached to DE-122 syringe injected into the anesthetized eye. Therefore, Step #3 and #4 of above DE-122 administration procedure will be skipped for the Sham injection.

To keep masking of the study, investigator and authorized staff must follow the points described in [Section 9.4](#).

10.8. Study Drug Accountability

The Principal Investigator is responsible for ensuring that an inventory is conducted upon receipt of the clinical supplies. The temperature recorder from the shipment will be deactivated and authorized study staff will verify that the temperature was maintained at 2° to 8°C (36° to 46°F) during transit.

The Principal Investigator will keep a current record of the inventory, storage conditions and dispensing of all study drugs. This record will be made available to Santen (or designee) for the purpose of accounting for all clinical supplies. Any significant discrepancy and/or deficiency must be recorded with an explanation.

All supplies sent to the Principal Investigator must be accounted for and in no case will study drugs be used in any unauthorized situation. It is the responsibility of the Principal Investigator to ensure that any used and unused supplies are available to Santen (or designee) throughout the study.

10.9. Study Drug Handling and Return

All investigational products including used/unused vials of DE-122/Lucentis® and syringes supplied by Santen/Representative will be fully accounted for by the monitor with the help of the unmasked person responsible for dispensing the DE-122 and will be returned to Santen/Representative or designee. Accountability will be documented by use of drug accountability forms.

Refer to Study Drug Manual for study drug handling.

11. ASSESSMENT OF EFFICACY

11.1. Best Corrected Visual Acuity (BCVA)

BCVA is the primary efficacy variable for this study, and mean change from baseline in BCVA at Week 24 is the primary efficacy endpoint. Proportion of subjects with BCVA Improvement of ≥ 15 letters, <15 letters change (stable) and loss of ≥ 15 letters from baseline at Week 24 are secondary endpoints.

The visual acuity will be recorded using the ETDRS chart and total number of letters at 4 meter and 1 meter will be recorded. If a subject could not read ETDRS chart, Finger Counts, Hand Motion, Light Perception, or No Light Perception will be recorded.

11.2. Central Subfield Thickness (CST), Macular Volume (MV), Central Retinal Lesion Thickness (CRLT)

CST, MV, and CRLT measured by SD-OCT are secondary efficacy variables, and change in CST, MV, and CRLT from baseline at Week 24 are secondary endpoints. All 3 parameters will be measured by the central reading center.

11.3. Lesion area

Change in total lesion area, total area of CNV, greatest linear dimension of the total lesion area by FA from baseline at Week 24 are secondary efficacy endpoints. Lesion areas will be measured by the central reading center.

12. ASSESSMENT OF SAFETY

12.1. Adverse Events

12.1.1. Definition of Adverse Events

An AE is any untoward medical occurrence in a subject administered a pharmaceutical product and which does not necessarily have a causal relationship with the study drug(s). An AE, therefore, can be an unintended sign (including an abnormal laboratory finding), symptom, or disease that has clinical significance and is temporally associated with the use of a medicinal (investigational) product, whether or not related to the medicinal (investigational) product.

In clinical studies, an undesirable medical condition occurring at any time, including baseline or pre-treatment period, may be recorded as an AE even if no study drug has been administered.

Any significant adverse change in a subject's condition from baseline, regardless of causality, is to be considered an AE, unless the change is determined to be a continuation of a pre-existing condition that is documented in the subject's medical history. However, a clinically significant worsening in severity, intensity, or frequency of a pre-existing condition may indicate an AE. In addition, all conditions that lead to hospitalizations, defined as an overnight hospital stay, are considered as AEs. This includes planned elective surgeries.

Lack of efficacy of the study drug(s) for the condition being investigated is not considered an AE unless a clinically significant change is assessed by the Clinical Investigator. An elective surgical procedure scheduled or planned prior to study entry is not considered an AE if an overnight hospital stay is not required, and the underlying diagnosis for which surgery is to be performed should be captured in the medical history as a pre-existing condition. The surgical procedure should also include the term "elective" in all reports.

12.1.1.1. Assessment of Adverse Events

Clinical Investigators will seek information on AEs at each subject contact. Subjects should be asked, using a general, non-direct question, if there has been any change in their general health. Direct questioning and examination should then be performed as appropriate.

Severity of the AE should be assessed according to the following criteria:

Mild: No interference with the subject's daily activities; no medical intervention/therapy required

Moderate: Possible interference with the subject's daily activities; no or minimal medical intervention/therapy required

Severe: Considerable interference with the subject's daily activities; medical intervention/therapy required

Regardless of severity, some AEs may also meet regulatory serious criteria. Refer to definitions and reporting of serious adverse events (SAEs) in [Section 12.1.2](#).

A Clinical Investigator who is qualified in medicine must make the determination of the relationship of the study drug(s) to each AE (related or not related). The Clinical Investigator

should decide whether, in his or her medical judgment, there is a reasonable possibility that the DE-122, Lucentis® or the Sham injection could have caused the AE/SAE based on facts, evidence, scientific rationales, and clinical judgment. When assessing causality, the Clinical Investigator may consider the following information when determining the relationship to the study drug(s) for each AE: mechanism of action, biologic plausibility, confounding risk factors (i.e., medical history, concomitant medications), temporal relationship, dechallenge/rechallenge, and lack of alternative explanation. It should be specified if the AE is related to the injection procedure and not the study drug.

- The AE may be recorded as **Related** to the study drug(s) if there is a plausible temporal relationship between the onset of the AE and administration of the study drug(s), and the AE cannot be readily explained by the subject's clinical state, concurrent illness, or concomitant therapies; and/or the AE follows a known pattern of response to the study drug(s); and/or the AE abates or resolves upon discontinuation of the study drug(s).
- Reporting the AE as **Not Related** to study drug(s), may be considered if, for example, there is good evidence that the AE has an etiology other than the study drug(s) (e.g., pre-existing medical condition, underlying disease, concurrent illness, or concomitant medication); and/or the AE has no plausible temporal relationship to administration of the study drug(s) (e.g., cancer diagnosed 2 days after dose of study drug(s)).

12.1.1.2. Reporting Adverse Events

AEs, whether spontaneously reported by the subject or noted by authorized study personnel, will be recorded in the subject's medical record and on the appropriate AE eCRF. Each recorded AE will be described by its duration (i.e., start and end dates), frequency, severity, regulatory seriousness criteria if applicable, suspected relationship to the study drug(s), relation to injection procedure, location, actions taken and outcome.

AEs that occur after any subject has provided written informed consent, before treatment, during treatment, or until study exit visit, whether or not they are related to the study, must be recorded. To improve the quality and precision of acquired AE data, Clinical Investigators should observe the following guidelines:

- Whenever possible, use recognized medical terms when recording. Do not use colloquialisms and/or abbreviations.
- If known, record the diagnosis (i.e., disease or syndrome) rather than component signs and symptoms and /or laboratory or test findings (e.g., record congestive heart failure rather than dyspnea, rales, and cyanosis, and enlarged heart on chest x-ray). However, other events that are considered unrelated to an encountered syndrome or disease should be recorded as individual AEs (e.g., if congestive heart failure and severe headache are observed at the same time and are clinically unrelated, each event should be recorded as an individual AE).

If the diagnosis is not known, then record the leading component sign, symptom or test finding and describe the other clinically related findings in the narrative description of the case. A suspected diagnosis can be used and described as such

(e.g., record suspected or probable myocardial infarction); this has to be updated in the clinical database once the diagnosis is confirmed.

AEs occurring secondary to other events (e.g., sequelae) should be identified by the primary cause. A primary AE, if clearly identifiable, generally represents the most accurate clinical term. If a primary AE is recorded, events occurring secondary to the primary event should be described in the narrative description of the case. For example:

The subject developed orthostatic hypotension and subsequently fainted and fell to the floor wherein she experienced a head trauma and neck pain.

The primary AE in this example is orthostatic hypotension. The fall, head trauma and neck pain should be described in the narrative description of the case.

- For intermittent events (e.g., intermittent headache), the event onset date should be recorded as the date the subject first started to experience the event and resolution date should reflect when the last occurrence resolved or stopped. Separate AEs for each event should not be recorded. For example, if a subject experienced headache on 14SEP2015 lasting for three hours, then subsequently experienced intermittent episodes of headache every day for approximately 3 hours until 21SEP2015, then the AE date of onset is 14SEP2015 and the resolution date is 21SEP2015.
- For intermittent events, record the maximum severity of the individual events. For example, if a subject complains of intermittent headaches for one week and the severity of each headache ranges from mild to moderate, then the severity would be moderate.
- For intermittent hospitalizations occurring for a primary AE (e.g., in a subject with multiple sclerosis, commonly known for its relapsing and remitting course, in some cases leading to multiple hospital confinements), the subsequent hospitalizations should be described in the narrative description of the case.
- If treatment was initiated, include the treatment and duration of the medication(s) in the eCRF.

12.1.2. Serious Adverse Events

SAEs are defined as any findings that suggest a significant hazard, contraindication, side effect, or precaution. Any adverse event is considered a serious adverse event if it results in any of the following outcomes:

- Death
- Life threatening:

A life-threatening event is any event that places the subject at immediate risk of death from the event as it occurred; it does not refer to an event that hypothetically might have caused death if it were more severe.

- Hospitalization, at the minimum an overnight stay
- A persistent or significant disability/incapacity

- A congenital anomaly/birth defect
- Other medically significant events:

Other medically significant events are events that may not result in death, be life-threatening, or require hospitalization but may be considered a serious adverse drug experience when, based upon appropriate medical judgment, they may jeopardize the subject and may require medical or surgical intervention to prevent one of the outcomes listed above.

- Sight threatening event:

A sight-threatening event is any event that places the subject at immediate risk of permanently losing vision in either eye as a direct result of the event. It is defined as a loss of ≥ 30 letters or 6 lines of vision from Baseline.

12.1.2.1. Reporting Serious Adverse Events

A SAE eCRF must be completed with as much information available within 24 hours of knowledge of the event.

To improve the quality and precision of acquired SAE data, Clinical Investigators should observe the following guidelines:

- **Death** - Death is an outcome of an event. The event that resulted in the death should be recorded and reported as a SAE.
- **Hospitalizations for Surgical or Diagnostic Procedures** - The illness leading to the surgical or diagnostic procedure should be recorded as the SAE, not the procedure itself. The procedure should be captured in the case narrative as part of the action taken in response to the illness.

When new significant information (including the outcome of the event) is obtained, the Clinical Investigator should enter the information directly into the eCRF within 24 hours or as soon as possible after knowledge of the information.

Depending on the nature and seriousness of the AE, Santen may request additional documentation, for example, copies of the ophthalmic and medical record of the subject as well as results of laboratory tests. If the subject was hospitalized, the site should summarize the hospital discharge summary and provide to Santen upon request.

12.1.2.2. Expedited Reporting of Serious Adverse Events

Santen (or designee) will provide the Principal Investigator with a reporting cover letter and an anonymized MedWatch 3500A or CIOMs form as appropriate for expedited reporting of SAEs to the IRB or IEC and the Philippines or the US regulatory agency. The Principal Investigator is responsible for receiving and reviewing expedited safety reports, submitting expedited safety reports to the IRB or IEC, and maintaining copies of expedited safety reports in the study records.

12.1.3. Events of Special Interest

Events of Special Interest (ESIs) are events that may require special attention for the purposes of on-going patient safety review during this study. The following are considered ESIs and should be reported on the appropriate eCRF with as much information as available within 24 hours of knowledge of the event:

- **Study medication administration error** – Study medication administration errors determined to be significant by the Clinical Investigator will be reported and evaluated as ESIs. Examples of study medication administration errors may include, but are not limited to: overdose of study medication and administration of study medication from an incorrect kit.
- **Pregnancy** - There are no controlled data with the investigational product in human pregnancy. It is required that females of childbearing potential use effective contraception during the study and recommended for 12 weeks after the completion of the study. Any pregnancy occurring during study treatment should be reported and the subject removed from the study. The subject should be followed until the end of pregnancy or until the end of the study, whichever is longer.
- **Ocular telangiectasia and bleeding events** – There is no data showing that the investigational product is related to these events. However, these are seen in the Osler-Weber-Rendu (OWR) syndrome, a genetic condition that causes endoglin dysfunction. DE-122 binds to and suppresses human endoglin, thus information about the ocular manifestations of OWR are of value in predicting possible ocular adverse events following IVT injection of DE-122. The following events will be considered ESIs and the subject followed until the end of the study or resolution of the event.
 - Ocular telangiectasia (Conjunctival and intraocular)
 - Intra- and extra-ocular bleeding (hemorrhage) not attributed to the injection procedure and/or AMD
 - Common systemic OWR signs: Epistaxis, gingival bleeding and mucocutaneous telangiectasia

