Several clinical trials for various cancer patients have been conducted by TRACON Pharmaceuticals, Inc. As of December 06, 2015, over 438 patients had been treated with TRC105. The majority of the patients have been Caucasian with ages ranging from 18 to 87 years. TRC105 has been well tolerated and exhibited a remarkably consistent adverse event profile, whether dosed as a single agent or dosed in combination with VEGF inhibitors or chemotherapy. Activity of TRC105 in combination has been particularly noteworthy and represents the current development strategy.

Santen is developing an ophthalmic formulation of TRC105, DE-122 injectable solution, suitable for intravitreal injection for the treatment of wet AMD.

Santen has conducted a Phase I/II, open-label, dose-escalating, sequential cohort study assessing the safety, tolerability, immunogenicity, and bioactivity of a single IVT injection of DE-122 injectable solution in the study eye of approximately twelve subjects with refractory wet AMD (Protocol 36-001). Four dose levels of DE-122 were assessed in this Phase I/II study, 0.5 mg/eye, 1.0 mg/eye, 2.0 mg/eye and 4.0 mg/eye. The doses selected for use in this study were based on the results from non-clinical studies. Additional information regarding the non-clinical studies is provided in the Investigator's Brochure.

As of July 2017, all 12 subjects completed the study. There were no reported SAEs. No dose-dependent events were reported and no new safety concerns were identified at all investigated doses. Ocular AEs were reported in 5 subjects (41.7%). Most common AE was Subconjunctival haemorrhage (3 subjects, 25%) and all were considered to be due to the injection procedure.

Santen believes that the Phase I/II study results mentioned above, in addition to the results of the non-clinical studies, supports the use of repeated IVT injections of the 2.0 mg and 4.0 mg concentrations of DE-122 in humans in the Phase II clinical trial (Protocol 36-002).

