7.2. Number of Subjects

Approximately 76 subjects (Arm 1: 17 subjects, Arm 2: 31 subjects, Arm 3: 28 subjects) with wet AMD will be enrolled at approximately 14 sites in the Philippines and the US. The final number of subjects enrolled may be adjusted up to 80 based on drop-out rate.

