16.7. Safety Analysis

All safety outcome measures will be summarized descriptively for the Safety Population. The safety outcome measures include adverse events (AEs), BCVA, slit-lamp biomicroscopy, indirect ophthalmoscopy, intraocular pressure (IOP), serum chemistry, hematology, urinalysis, vital signs, physical examination, fundus photography, fluorescein angiography, EKG and pregnancy.

AEs will be coded using the Medical Dictionary for Regulatory Activities (MedDRA).

Subjects with any AEs will be tabulated by system organ classification and preferred term specified in the MedDRA. Similarly, subjects with any ocular and non-ocular AEs and ESIs will be tabulated separately. AEs, ocular and non-ocular, as well as ESIs will also be summarized by relationship to treatment and maximum severity. In addition, SAEs and discontinuations due to AEs will be summarized.

Ocular safety outcome measures will be summarized using descriptive statistics.

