#### 4.3.1.5. Events of Special Interest

*Events of special interest (ESI)* such as pregnancy, study medication administration error, ocular telangiectasia and bleeding events will be identified throughout the study. An event will be counted as ESI if the Clinical Investigator selected “Yes” to the AE eCRF question “Is it a protocol defined Event of Special Interest (ESI)?”

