### **9.1. Adverse Event**

Subjects with any AE(s), SAE(s), SAR(s), serious SAR(s) and ESI(s) will be tabulated for each actual treatment received. Besides the overall AE summary, subjects with any AE(s) will be tabulated by SOC and PT specified in MedDRA Version 20.0. Subjects with any AE(s) will also be tabulated by SOC, PT and maximum severity. A subject who experienced multiple AEs within a SOC or PT will be counted only once at the maximum severity for that SOC or PT. SAEs, SARs, and Serious SARs will be tabulated similarly.

Summaries for ocular AEs and non-ocular AEs will also be performed. Ocular AEs, ocular SAEs and ocular SARs will be summarized for study eyes and fellow eyes separately. Any ocular AE that occurred simultaneously to both eyes will be counted once for both the study eye and the fellow eye.

All AE tabulations will be performed on the Safety population for the On-treatment period, Follow-up period and entire study.

AEs, AEs leading to death, AEs leading to discontinuation, SAEs, and ESIs, if any, will be listed separately.

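### The ocular-bleeding ESI count is filtered by attribution and can understate bleeding on DE-122; separately, SAP 9.1 omits the ESI summary that Protocol 16.7 states

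*Protocol*

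**What the plan says.** Protocol 12.1.3 derives its bleeding and telangiectasia ESIs from Osler-Weber-Rendu (OWR) syndrome: "DE-122 binds to and suppresses human endoglin, thus information about the ocular manifestations of OWR are of value in predicting possible ocular adverse events". Three items follow. Ocular telangiectasia is listed without condition. Ocular bleeding is conditional: "Intra- and extra-ocular bleeding (hemorrhage) not attributed to the injection procedure and/or AMD". The third item is again unconditional: "Common systemic OWR signs: Epistaxis, gingival bleeding and mucocutaneous telangiectasia". The section presents ESIs as a tool for ongoing safety review, with reporting within 24 hours.

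SAP 4.3.1.5 states that ESIs "such as pregnancy, study medication administration error, ocular telangiectasia and bleeding events will be identified throughout the study". It counts an event only if the investigator answers yes to the AE form's question on protocol-defined ESIs, so the condition in 12.1.3 carries through to the analysis.

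Protocol 16.7 says that ESIs get their own tabulation, and adds: "AEs, ocular and non-ocular, as well as ESIs will also be summarized by relationship to treatment and maximum severity". SAP 9.1 provides the number of subjects with any ESI by treatment received, and a listing. Its breakdown by system organ class (SOC), preferred term (PT) and maximum severity covers all AEs and is then extended: "SAEs, SARs, and Serious SARs will be tabulated similarly". ESIs are not in that extension, and no ESI table by relationship is planned.

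On the sponsor's earlier single-injection study of 12 subjects, Protocol 5 reports: "Most common AE was Subconjunctival haemorrhage (3 subjects, 25%) and all were considered to be due to the injection procedure".

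**The concern.** There are two separate points.

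1. The ESI category is where a reader will look for the bleeding risk that the protocol itself predicts from the mechanism. For ocular bleeding, each event enters only after an investigator has set aside both the injection and the AMD as causes. All study eyes have wet AMD (Protocol 8.1) and are scheduled for six Lucentis injections; DE-122 eyes are scheduled for six further needle entries. One of the two exempting causes is therefore nearly always plausible. A low or zero ocular-bleeding ESI count would say little about how often DE-122 eyes bled.

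2. The SAP reports ESIs in less detail than the protocol states. Its single count mixes bleeding with pregnancy and medication errors, so even the bleeds that are ticked cannot be read from a summary table.

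At stake is how clearly the report describes a named, mechanism-based risk in a trial with 17 control subjects.

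**Working it through.** **Inputs**
- Phase I/II: 3 of 12 subjects with subconjunctival haemorrhage, all attributed to the procedure (Protocol 5).
- DE-122 subjects: 31 + 28 = 59 (Protocol 7.2).
- Share *f* of bleeds attributed to the injection or AMD: not given for this trial. The only value in the documents is 3 of 3 (100%) in Phase I/II, so *f* is varied as an assumption.

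**Step 1: the protocol's figure.** 3/12 = 25%, as stated. The exact (Clopper-Pearson) 95% interval is 5.5% to 57.2%.

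**Step 2: the 12.1.3 condition applied to those data.** All 3 bleeds were attributed to the procedure, so 3 − 3 = 0 would be ESIs.

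**Step 3: projection to this trial.** Let *r* be the proportion of DE-122 subjects with an ocular bleed, with one attribution per bleeding subject and independent subjects.
- Expected subjects with a bleed = 59 × *r*. At 25% this is 14.75; at the interval limits it is 3.2 and 33.7.
- Expected ocular-bleeding ESIs = 59 × *r* × (1 − *f*).
- Chance of none = (1 − *r*(1 − *f*))^59. Example: *r* = 0.25 and *f* = 0.95 give (1 − 0.0125)^59 = 0.48.

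| Share attributed *f* | Expected ESIs, *r* = 25% | Chance of zero, *r* = 25% | Chance of zero, *r* = 5.5% | Chance of zero, *r* = 57.2% |
|---|---|---|---|---|
| 100% | 0 | 1.0 | 1.0 | 1.0 |
| 95% | 0.74 | 0.48 | 0.85 | 0.18 |
| 90% | 1.47 | 0.22 | 0.72 | 0.03 |
| 80% | 2.95 | 0.05 | 0.52 | <0.001 |
| 50% | 7.38 | <0.001 | 0.19 | <0.001 |

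Zero is realistic when attribution is near complete or bleeding is uncommon. It is not automatic.

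**Step 4: the unfiltered items.** For epistaxis and gingival bleeding, the chance of none in 59 is (1 − *p*)^59: 0.30 at a true rate of 2%, 0.05 at 5% and 0.002 at 10%. An appreciable excess there would be expected to show among the ESIs.

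**Step 5: Protocol 16.7 beside SAP 9.1**

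| ESI output | Protocol 16.7 | SAP 9.1 |
|---|---|---|
| Own tabulation | Yes | One any-ESI count per treatment, plus a listing |
| By relationship to treatment | Yes | No |
| By maximum severity | Yes | No |

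This gap needs no assumption. It is also independent of Steps 2 and 3: a missing breakdown cannot lower a count, and restoring it would not recover bleeds that were never ticked.

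**Step 6: where unticked bleeds still appear.** SAP 9.1 tabulates all AEs by treatment received, by SOC and PT and by maximum severity, and summarises ocular AEs separately for study and fellow eyes, with no attribution condition. SAP 9.3 tabulates changes from normal to abnormal in retina, macula and choroid. The SAP has no row grouping haemorrhage terms. It also has no table using relation to the injection procedure, although Protocol 12.1.1.2 and 12.2.13 have that recorded for each AE.

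**The case against.** The strongest reply is that ESIs exist for prompt safety review, and that keeping expected procedural and disease-related bleeds out of 24-hour reporting is a deliberate choice. That stands, and it is a reason to leave the definition alone. It does not make the resulting count a good measure of bleeding.

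Four stronger readings are tempting, and the documents do not support them:

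- *All bleeding is filtered.* A reader might infer this from the conditional item. Ocular telangiectasia, epistaxis, gingival bleeding and mucocutaneous telangiectasia carry no condition.
- *The SAP omission would produce a zero count.* Any zero would come from the definition and the investigator's tick.
- *A bleeding excess would go unreported.* The AE tables described above would show it by arm, though spread over preferred terms. The Phase I/II haemorrhages were themselves reported as the most common AE despite being attributed to the procedure.
- *The projected 15 or so bleeds are a concealed drug effect.* The earlier study was uncontrolled, gave one injection and spanned four doses. The figure is an expected number of bleeds, with no control rate to compare.

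A further objection stands in full. Under Protocol 10.7 the sham does not penetrate the eye, so DE-122 eyes receive a second needle entry at each injection visit. Comparing study-eye bleeds by arm without attribution therefore mixes drug with puncture.

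**Conclusion.** Both points hold, as a reporting weakness that is cheap to correct. On the first, the ocular-bleeding ESI count can understate bleeding on DE-122. At a 25% rate in 59 subjects the chance of a zero count runs from 1.0 with complete attribution, as in Phase I/II, to 0.05 with 80% attributed. This rests on carrying over a rate from 12 single-injection subjects, whose interval is wide, and on an assumed attributed share. The loss is of a clear grouped view; the events themselves remain in the AE tables.

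On the second, SAP 9.1 falls short of Protocol 16.7 on the face of the two texts, and the SAP gives no reason.

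**What to change.** Leave the Protocol 12.1.3 reporting definition unchanged. In SAP 9.1:

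- Add a by-arm table of all haemorrhage and telangiectasia AEs, including epistaxis, gingival bleeding and mucocutaneous telangiectasia. Select them by a preferred-term list fixed before unmasking, regardless of ESI tick or attribution. Show study eye, fellow eye and non-ocular events separately, put subconjunctival haemorrhage on its own row, and split by the recorded relation to the injection procedure.
- Restore the ESI tables by relationship and maximum severity from Protocol 16.7. Also show bleeding and telangiectasia ESIs apart from pregnancy and medication errors; this separation goes beyond what 16.7 asks.
- State with the haemorrhage table that DE-122 eyes have a second needle entry per injection visit, so a study-eye excess cannot by itself be assigned to the drug rather than the puncture. The fellow-eye row does not resolve this, because that eye receives neither DE-122 nor the extra puncture.

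The cost is one term list, one new table and the ESI tables already stated in the protocol, all from AE data already collected. The downside is that the pooled row will contain procedural bleeds; the separate subconjunctival row and the split by procedure relation make these visible but do not remove the confounding.
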